10.5 Missing Data

Every effort will be made to minimize the amount of missing data. Recognizing the difficulty of avoiding some missing data, however, data imputation methods with sensitivity imputation analyses will be specified in the Statistical Analysis Plan. Subjects with missing effectiveness data will be assumed to have missing data at random and will be imputed by random selection with replacement of data from subjects with pre- and post-intervention measurement of thrombus removal. The robustness of the multiple imputation outcome will be tested with a tipping point analysis encompassing all possible imputation outcomes.

10.6 SAFETY PERFORMANCE GOAL DERIVATION

The primary safety endpoint of 30-day MAE was assessed from published studies that treated DVT with pharmacologic means or with other thrombectomy devices. The weighted average MAE rate was 23.8%. Using a 10% margin and rounding to the nearest percent, the performance goal for the primary safety endpoint, 30-day freedom from MAE, was 34%. A detailed analysis of the safety performance goal will be described in the statistical analysis plan.

10.7 EFFECTIVENESS PERFORMANCE GOAL DERIVATION

The primary effectiveness endpoint of Technical Success was assessed from published studies that treated DVT with pharmacologic means or with other thrombectomy devices). The weighted average Technical Success rate was 39.3%. Using a 10% margin and rounding to the next percent, the performance goal for the primary effectiveness endpoint of Technical Success was 30%. A detailed analysis of the effectiveness performance goal will be described in the statistical analysis plan.

10.8 SAMPLE SIZE

The performance goal of 34% has been established for the primary safety endpoint, based on a one-sided 97.5% exact binomial test. The 30-day MAE rate is anticipated to be approximately 20%. Under this assumption, the required sample size to achieve a level of 82% power is 86 subjects (**Table 2**). Assuming 5% attrition over 30 days, enrollment of 91 subjects is necessary for the Primary Analytic Dataset.

Table 2. Sample Size - Primary Safety Endpoint

| Measure | |
|------------------------------|-------------------------------|
| Performance goal | 34% |
| Anticipated freedom from MAE | 20% |
| Significance level | .025 |
| Statistical test | One-sided exact binomial test |
| Desired power level | 82% |

| Required sample size prior to 5% 30-day attrition rate | 86 |
|--|----|
| Required sample size after attrition adjustment | 91 |

A performance goal of 30% has been established for the primary effectiveness endpoint. Anticipating an actual Technical Success rate of approximately 50%, and based upon a one-sided 97.5% exact binominal test, the required sample size to achieve a level of 97% power is 85 subjects (**Table 3**). Since the primary effectiveness endpoint is determined at the time of the index procedure, no attrition has been considered for lost to follow-up or other censoring events. However, the effectiveness endpoint is evaluated in the Primary Analytic Effectiveness cohort, and it is assumed that 3% of enrolled subjects will be treated for DVT in the absence of core laboratory-assessed visible thrombus in the TVS. Assuming a 3% attrition rate for subjects without thrombus, enrollment of 88 subjects will be necessary.

Table 3. Sample Size - Primary Effectiveness Endpoint

| Measure | |
|--|-------------------------------|
| Performance goal | 30% |
| Anticipated technical success rate | 50% |
| Significance level | .025 |
| Statistical test | One-sided exact binomial test |
| Desired power level | 97% |
| Required sample size prior to 3% attrition for subjects without thrombus | 85 |
| Required sample size after attrition adjustment | 88 |

The required sample size is greater for the primary safety endpoint; 91 vs. 88 subjects. Thus, a total of 91 subjects will be enrolled in the Primary Analysis dataset; providing approximately 91 subjects in the Primary Safety cohort and 88 subjects in the Primary Effectiveness cohort for the primary safety and effectiveness analyses, respectively. The overall power of the study is 80%.

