5.1. Sample Size

The performance goal of 34% has been established for the primary safety endpoint, based on a one-sided 97.5% exact binomial test. The 30-day MAE rate is anticipated to be approximately 20%. Under this assumption, the required sample size to achieve a level of 82% power is 86 subjects (**Table 1**).

Assuming 5% attrition over 30 days, enrollment of 91 subjects is necessary for the Primary Analytic Dataset.

Table 1. Sample Size - Primary Safety Endpoint

Measure	
Performance goal	34%
Anticipated freedom from MAE	20%
Significance level	.025
Statistical test	One-sided exact binomial test
Desired power level	82%
Required sample size prior to 5% 30-day attrition rate	86
Required sample size after attrition adjustment	91

A performance goal of 30% has been established for the primary effectiveness endpoint. Anticipating an actual Technical Success rate of approximately 50%, and based upon a one-sided 97.5% exact binomial test, the required sample size to achieve a level of 97% power is 85 subjects (**Table 2**). Since the primary effectiveness endpoint is determined at the time of the index procedure, no attrition has been considered for lost to follow-up or other censoring events. However, the effectiveness endpoint is evaluated in the Primary Analytic Effectiveness cohort, and it is assumed that 3% of enrolled subjects will be treated for DVT in the absence of core laboratory-assessed visible thrombus in the TVS. Assuming a 3% attrition rate for subjects without thrombus, enrollment of 88 subjects will be necessary.

Table 2. Sample Size - Primary Effectiveness Endpoint

Measure	
Performance goal	30%
Anticipated technical success rate	50%
Significance level	.025
Statistical test	One-sided exact binomial test
Desired power level	97%
Required sample size prior to 3% attrition for subjects without thrombus	85
Required sample size after attrition adjustment	88

The required sample size is greater for the primary safety endpoint; 91 vs. 88 subjects. Thus, a total of 91 subjects will be enrolled in the Primary Analysis dataset; providing approximately 91 subjects in the Primary Safety cohort and 88 subjects in the Primary Effectiveness cohort for the primary safety and effectiveness analyses, respectively. The overall power of the study is 80%.

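### The stated powers (82%, 97%, overall 80%) are labelled exact binomial but match a normal approximation; the named exact test gives about 81%, 96% and, if the endpoints are independent, 78%

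*Protocol*

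**What the plan says.** Protocol 10.8 and SAP 5.1 carry the same calculation.

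- **Safety.** The Protocol says "The performance goal of 34% has been established for the primary safety endpoint, based on a one-sided 97.5% exact binomial test", and "The 30-day MAE rate is anticipated to be approximately 20" percent. From this, "the required sample size to achieve a level of 82% power is 86 subjects" (SAP 5.1). With attrition, "Assuming 5% attrition over 30 days, enrollment of 91 subjects is necessary for the Primary Analytic Dataset".
- **Effectiveness.** "A performance goal of 30% has been established for the primary effectiveness endpoint", the true success rate is taken as about 50%, and "the required sample size to achieve a level of 97% power is 85 subjects". Allowing 3% for subjects without core-laboratory thrombus brings this to 88.
- **Test.** Both sample-size tables name the test as "One-sided exact binomial test" at .025.
- **Overall.** The last paragraph of the section expects about 91 safety and 88 effectiveness subjects and ends: "The overall power of the study is 80" percent.

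Protocol 10.4 makes the study a success only if both endpoints meet their goals. Neither document says how the overall figure was obtained or what dependence between the endpoints was assumed.

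**The concern.** A power labelled as exact binomial should be reproducible from the binomial distribution, and these are not. The 97% at 85 subjects is the clearest miss. The overall figure inherits the difference, and it is the one the study relies on, because either endpoint alone can fail the trial.

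The approximation also hides how exact power behaves. Under the normal formula, safety power rises smoothly with the number evaluable, from 82.2% at 86 to 84.6% at 91. Exact power moves in a saw-tooth, because the pass mark is a whole number of events, and it is lower at 91 than at 86. A reader of the plan cannot see this.

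**Working it through.** **Inputs** (Protocol 10.8, SAP 5.1): safety null 34%, true MAE rate 20%; effectiveness null 30%, true success rate 50%; one-sided alpha 0.025; attrition 5% and 3%; cohorts 91 and 88. The safety table labels the 20% as freedom from MAE. I take it as the MAE rate, as the text does.

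**1. Reproducing the plan's figures.** The one-sample normal approximation, with null variance in the critical value and alternative variance in the denominator, is

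power = Φ{ (|p0 − p1| − 1.96·√[p0(1−p0)/n]) / √[p1(1−p1)/n] }.

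- Safety, n = 86: (0.14 − 1.96 × 0.05108) / 0.04313 = 0.925, so power is 82.2%. At n = 85 it is 81.7%, so 86 is the smallest n reaching 82%.
- Effectiveness, n = 85: (0.20 − 1.96 × 0.04971) / 0.05423 = 1.891, so power is 97.1%. At n = 84 it is 96.9%, so 85 is the smallest n reaching 97%.
- Overall: 0.8224 × 0.9707 = 79.8% (or 0.82 × 0.97 = 79.5%). Both round to 80%.
- Attrition: 86/0.95 = 90.5, giving 91; 85/0.97 = 87.6, giving 88.

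Every stated figure is recovered.

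**2. The test the plan names.** Safety passes if the MAE count is at most c, the largest value with P(X ≤ c | n, 0.34) ≤ 0.025; power is P(X ≤ c | n, 0.20). Effectiveness passes if successes number at least r, the smallest value with P(X ≥ r | n, 0.30) ≤ 0.025; power is P(X ≥ r | n, 0.50).

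| Endpoint | n | Pass mark | Actual alpha | Exact power | Stated |
|---|---|---|---|---|---|
| Safety | 86 | ≤ 20 | 0.0209 | 81.5% | 82% |
| Safety | 91 | ≤ 21 | 0.0162 | 80.8% | – |
| Effectiveness | 85 | ≥ 35 | 0.0185 | 95.9% | 97% |
| Effectiveness | 88 | ≥ 36 | 0.0191 | 96.5% | – |

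Exact safety power for n = 86 to 91 is 81.5%, 79.9%, 78.3%, 83.7%, 82.3% and 80.8%.

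**3. Overall power, assuming independent endpoints.**

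- 86/85: 0.8148 × 0.9590 = 78.1%.
- 91/88: 0.8084 × 0.9653 = 78.0%.
- Averaged over binomial retention of 91 subjects at 95% (safety) and 97% (effectiveness): 0.8054 × 0.9654 = 77.8%.

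**4. Without independence.** At 86/85, joint power must lie between 0.8148 + 0.9590 − 1 = 77.4% and the smaller of the two powers, 81.5%. Simulation with a per-subject correlation between MAE-free status and technical success of −0.2, 0, 0.2 and 0.4 (an assumed range) gives 77.7%, 78.2%, 78.7% and 79.3%.

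**The case against.** The strongest reply is that the gaps are smaller than the uncertainty in the inputs. The plan calls its rates approximate. At n = 86, a true MAE rate of 19.5% gives 84.5% exact safety power and 20.5% gives 78.2%, so half a point in the assumption matters more than the choice of formula. At the 88 subjects the plan expects to analyse, effectiveness power is 96.5%, which rounds to the stated 97%. The overall 78% depends on independence and on the evaluable numbers: 89/88 gives 0.8371 × 0.9653 = 80.8%, and the bounds at 86/85 include 80%. All of this stands, and it is why the point is minor. It does not make 85 subjects deliver 97% under the named test, and the attrition-averaged figure under independence is still below 80%.

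Three stronger readings are tempting and not supported.

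- **That effectiveness needs 89 subjects rather than 85.** 89 is the first n with exact power of at least 97% (97.2%), but power falls back to 96.4% at 90 and 96.9% at 93, and stays above 97% only from 94. It is one tooth of the saw, not a threshold.
- **That safety does not drive the sample size.** Safety is clearly the less powerful endpoint around the planned size, for example 80.8% against 97.1% if all 91 were evaluable for both. The plan's conclusion on this holds.
- **That the 80% is known to be the product of the approximate powers.** The match is close, but the documents do not give the derivation.

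**Conclusion.** The point holds as a minor correction. The sample-size pairs match a normal approximation but are presented as exact binomial results. Under the exact test, power is 81.5% for safety at 86 (78% to 84% over 86 to 91), 95.9% to 96.5% for effectiveness at 85 to 88, and about 78% overall against the stated 80%. The overall figure rests on independent endpoints and on the plan's own true rates; the positive correlations tried raise it to at most 79.3% at 86/85.

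A reader might infer that the trial is materially underpowered or must enrol more primary-analysis subjects. The documents do not support that. The shortfall is about 2 points overall, and the pass marks keep each test below 0.025, so type I error is unaffected.

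**What to change.** Keep 91 subjects. In Protocol 10.8 and SAP 5.1, restate the powers for the exact test:

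- Safety: about 81% (81.5% at 86 evaluable, 80.8% at 91), with a note that it ranges from 78% to 84% over 86 to 91.
- Effectiveness: 95.9% at 85 and 96.5% at 88.
- Overall: about 78%, with the independence assumption written beside it.

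Remove the statement that 85 subjects give 97% power. Adding the pass marks (at most 20 of 86 or 21 of 91 MAEs; at least 36 of 88 successes) is optional but would let a reader check the figures.

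The cost is wording and table edits in two documents and a slightly less favourable stated power. Enrolment, endpoints and the analysis do not change.

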10.9 CONTINUED ENROLLMENT BEYOND THE PRIMARY ANALYSIS DATASET

Once the required number of subjects for the Primary Analysis dataset are enrolled, subject enrollment will continue in the Full Analysis dataset. In total, 500 subjects will be enrolled in the study, with a subset of 91 subjects in the Primary Analysis Dataset. The aggregate Full Analysis dataset will comprise the 91 Primary Analysis cohort and the 409 subjects not in that cohort. Enrollment of the 500 subject aggregate Full Analysis population will allow descriptive safety and effectiveness analyses on a larger dataset than would the Primary Analysis dataset alone, with subgroup analyses as described in Section 10.11.

Subjects who do not fit the criteria for the Primary Analysis Dataset will be enrolled in the Full Analysis Cohort in parallel (see Section 6.4). It is likely that the Primary Analysis Cohort will be enrolled before 409 subjects have been enrolled in the Full Analysis Cohort. Once enrollment in the Primary Analysis Cohort is fully accrued, subjects that subjects that would have met the criteria for inclusion into this subset will continue to be enrolled as part of the Full Analysis dataset.

10.10 DEMOGRAPHICS AND BASELINE CHARACTERISTICS

The baseline demographics and anatomic characteristics of the treatment group will be presented with descriptive statistics.

10.11 SUBGROUP AND OTHER ANALYSES

The following subgroups will be analyzed:

- Acute (≤14 days) versus subacute (>14 days ≤6 weeks) versus chronic (>6 weeks)
- Iliofemoral versus femoropopliteal
- Men versus women
- Old versus younger (≥65 years, <65 years)
- Obese versus not obese (BMI ≥30 kg/m², >30 kg/m²)

10.12 DATA POOLABILITY ASSESSMENT

Poolability of data across clinical study sites is justified on a clinical basis (i.e. all study sites use the same protocol), the Sponsor monitors the site for protocol compliance, and the data gathering instruments are identical. The FDA also requires a statistical assessment of poolability. This is done by comparing the baseline characteristics across study sites. For categorical baseline variables, such as sex, a generalized Fisher's exact test or equivalent test will be used and for quantitative variables, parametric or non-parametric analysis of variance (general linear models or an equivalent procedure) will be used.

The above statistical analyses do not result in an impediment to pooling, but rather assess the balance of baseline covariates across study sites. If any baseline covariate is found to be statistically significant by this process, generalized linear mixed model (GLMM) will be used to assess site heterogeneity. This is done by using site a random effect and further quantifying the heterogeneity in terms of Higgin & Thompson's *I*² index.

It may be necessary to combine two or more low enrolling study sites into pseudo-sites to allow these analyses. Sites with fewer than six subjects will be ranked by enrollment from low to high. Starting from the lowest enrollment site, sites will be combined into a pseudo site until the combined size reaches the median enrollment among all sites. This process will be repeated until all resulting sites have enrollment equal to or greater than six subjects. This will be done in a manner to preserve the structure of the study and prevent bias.

Baseline characteristics to be considered as possible covariates will include:

- Age
- Sex
- Coronary artery disease
- Chronic obstructive pulmonary disease
- Myocardial infarction
- Hyperlipidemia
- Cerebrovascular accident
- Hypertension
- Diabetes
- History of tobacco use
- Duration of symptoms
- Isolated iliofemoral DVT versus iliofemoral and distal DVT
- History of hypercoagulable state

Obesity

If there are relatively few missing data points (e.g., <10%) for a given variable, a simple imputation using the mean (for continuous variables) or median (for dichotomous or categorical variables) of the non-missing values will be done. If there are >10% missing, the variable will be excluded from the imputation analysis.

Poolability analysis will also be performed on the primary endpoints comparing across sites after adjusting for covariates difference. Logistic regression model will be utilized to include unbalanced covariates and site as an independent variable, and the study outcome as dependent variable to assess outcome difference. If the p-value of site effect is less than 0.10, further analyses will be undertaken to investigate the imbalance of the study outcome.

11 STUDY MANAGEMENT CONSIDERATIONS

11.1 DATA MANAGEMENT: CLINICAL DATA

The Sponsor and/or designee will be responsible for the processing and quality control of the data. All source data, CRFs, copies of protocols and protocol amendments, correspondence, subject identification lists, informed consent forms, and other essential documents must also be retained for a period of at least 2 years after study completion or closure.

No study document or image will be destroyed without prior written agreement between the Sponsor and the Investigator prior to conclusion of the retention period (see Section 12.4.2). Should the Investigator wish to assign the study records to another party or move them to another location, advance written notice must be given to the Sponsor.

11.2 PROTOCOL MODIFICATIONS

No changes from the final approved protocol will be initiated without the IRB's prior written approval of the amendment. The Principal Investigator will acknowledge an amendment by signing the Protocol Signature Page.

11.3 PROTOCOL DEVIATIONS

A protocol deviation is the non-adherence to or divergence from the protocol-specific required study procedures. For example, violations of the inclusion and exclusion criteria, improper or lack of consent, and lack of IRB approval, would all be considered protocol deviations.^g

Given that this is a registry study capturing real-world data and standard of care may differ amongst sites, deviations from the protocol with regards to specific procedures, testing, and data points collected, as well as visit windows, will not be captured as a protocol deviation. However, the Sponsor will address any trends in omissions and deviations observed and work with the investigational site to improve data collection where possible.

^g Subject eligibility for the study is determined by site-measured anatomic criteria, not by core laboratory values. For this reason, core laboratory-determined anatomic measurements from the baseline, pre-interventional angiogram are not part of subject eligibility determination and are not considered protocol deviations.

A record of reportable protocol deviations, as described above, will be maintained, and reviewed throughout the conduct of the study. The Sponsor will address deviations and take appropriate corresponding action. Continued non-compliance with the study protocol may lead to termination of the Investigator's participation in the study.

11.4 Information to Study Personnel

The Investigator is responsible for giving information about the study to all staff members involved in the study or in any element of subject management, both before starting the study and during the course of the study (e.g., when new staff become involved). The Investigator must ensure that all study staff members are qualified by education, experience, and training to perform their specific responsibilities.

The Sponsor or designee is responsible for explaining the protocol to all study staff, including the Investigator, and for ensuring their compliance with the protocol throughout the study. Additional information will be made available during the study when new staff become involved in the study, and as otherwise agreed upon with either the Investigator or the Sponsor or designee.

12 STUDY ADMINISTRATION

12.1 SITE INITIATION

A Site Initiation Visit (SIV) will be conducted by the Sponsor or designee in-person or via teleconference to ensure proper training of the Investigator and study staff members regarding the study protocol and data collection, as well as to ensure regulatory requirements are fulfilled prior to enrollment of the first study subject at a site.

12.2 STUDY MONITORING

Interim monitoring visits may be conducted by the Sponsor or designee in-person or remotely to ensure compliance with the protocol, and other written instructions and regulatory guidelines according to the study-specific monitoring plan.

The main responsibilities of the Monitor are to ensure adherence to the protocol; to verify all data are correctly and completely recorded and reported; and confirm that informed consent is obtained and recorded for each subject before any medical record or personal health information is shared with any study representatives. The Investigator and assisting staff must agree to cooperate with the Monitor or Sponsor representative to resolve any study-related problems, errors, or possible misunderstandings concerning the findings detected during these monitoring visits or data review.

12.3 STUDY TERMINATION

Inari Medical and applicable regulatory authorities have the right to terminate the entire study or a specific study site at any time. Situations that could warrant study termination include, but are not limited to:

- Increased incidence of adverse experiences and/or the severity of such, suggestive of a potential, devicerelated health hazard
- Insufficient subject enrollment
- Recurrent protocol non-compliance, violations, or deviations

- Inaccurate, incomplete, and/or untimely data recording or query responses (>5 business days) on a recurrent basis
- Lack of cooperation with monitoring visits (e.g., failure to adequately prepare for visits, address action items from one visit to the next, or provide access to medical records)

12.4 DATA HANDLING AND RECORDKEEPING

12.4.1 Completing, Signing and Archiving Case Report Forms

Clinical study data will be collected using electronic case report forms (eCRFs). A web-based electronic data capture (EDC) database will be used to record and manage study data. eCRF completion guidelines, the instructions for electronic data-entry will be developed in conjunction with the Sponsor and/or the EDC vendor. All eCRFs must be kept in good order and updated so they always reflect the latest observations on the subjects participating in the study.

The Investigator will sign the appropriate eCRF pages and source documentation. Pertinent eCRF corrections will be made electronically and signed electronically by the Investigator. An embedded audit trail will capture the date, time and user making updates and changes to the electronic data.

Because it is important to have proper data collection in a timely manner, within 5 business days of the study visit/assessment, the Investigator/Study Coordinator shall complete the eCRFs. When the Sponsor or designee requests additional data or clarification of data for the eCRF, the request must be answered satisfactorily in a timely manner.

